7.9.2 WBCT Bilateral Hand/Wrist and Knee Growth Plate Morphology Assessment

Imaging was performed for pediatric subjects, i.e. subjects <18 years old who underwent WBCT scan at study enrollment and during regularly scheduled follow-up visits thereafter. Although the WBCT scans obtained in the trial are used primarily to quantify change in HO volume, they will also be used to assess bone safety, including bilateral hand/wrist and knee growth plate abnormalities on all subjects age < 18 years.

The following abnormalities of the Epiphyseal Growth Plates assessed from WBCT will be assessed:

- EGP Abnormality Location: Wrist or Knee
- Calcinosis
- Cupping
- Dense Metaphyseal Lines
- Frayed Metaphyseal Edge
- Under Mineralisation or Osteopenia of the Adjacent Growing Bone
- Sclerosis of the Adjacent Growing Bone

- Widening of the Epiphyses
- Other

Counts of abnormalities of epiphyseal growth plates (yes/no/not evaluable) detected will be summarized for each timepoint. (selecting the “last case” in the hierarchy for each abnormality, in order of the terms listed below):

- Open Epiphyseal Growth Plates
 - Yes, Open
 - Yes, Partially Closed
 - No (Closed)
 - Not Evaluable
 - Missing
- Open Epiphyseal Growth Plates Location
 - Wrist or Knee
 - Wrist and Knee
 - Wrist Only
 - Knee Only
 - Not Evaluable
 - Closed

Counts of abnormalities detected will be summarized as follows:

- Any Abnormality of Epiphyseal Growth Plates
 - Yes
 - No
 - Not Evaluable

Frequency of each abnormality for each timepoint and changes from baseline and from prior timepoint will also be summarized.

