7.9.1 Knee and Hand/Wrist Radiographs

Subjects under the age of 18 years at the time of enrollment into Study PVO-1A-202 or PVO-1A-201 with open epiphyseal growth plates will undergo knee and hand/wrist radiographs (AP view) for assessment of epiphyseal growth plate.

Knee and hand/wrist radiographs will be performed remotely (eg, at a local medical facility) for subjects who are unable or unwilling to attend site visits. Once a subject has achieved 100% skeletal maturity (as confirmed by radiography), knee and hand/wrist radiographs will no longer be required.

Summary statistics of bone age and chronological age (values and changes from baseline) for subjects < 18 years will be calculated at each scheduled visit for Enrolled Population. Changes in bone age will be plotted over time.

Two independent radiology reviewers will qualitatively assess the hand/wrist and knee growth plate for abnormalities listed below. Discrepancies in the reads will be adjudicated.

The following abnormalities of the Epiphyseal Growth Plates assessed from X-ray will be assessed:

- EGP Abnormality Location: Wrist or Knee
- Calcinosis
- Cupping
- Dense Metaphyseal Lines
- Frayed Metaphyseal Edge
- Under Mineralisation or Osteopenia of the Adjacent Growing Bone
- Sclerosis of the Adjacent Growing Bone
- Widening of the Epiphyses
- Other

Summary tables of growth plate abnormalities identified in radiographs will include the following:

- Number and percent of subject with epiphyseal growth plates open (by hand/wrist and/or knee).
- Number and proportion of subjects with any abnormality at each visit, for each specific abnormality (e.g. growth recovery lines, Sclerosis, Under mineralization, etc.).
- Number and proportion of subjects with any change from baseline and from prior timepoint for hand/wrist and knee by each abnormality for each visit.
- Number and proportion of subjects with any change from baseline and from prior timepoint for hand/wrist and knee by each abnormality across all post-screening visits. For summaries across all timepoints, the worst case for a given subject will be used in the analysis.
- Number and proportion of subjects with any change from baseline and from prior timepoint for hand/wrist and knee across all abnormalities and post-screening visits. For summaries across all abnormalities and timepoints, the worst case for a given subject will be used in the analysis.

Premature growth plate closure

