Listings of all subjects with premature growth plate closure will be provided.

Analyses of Knee Alignment

Distal femoral angle and premature closure of the growth plate will also be summarized for subjects < 18 years old in Enrolled Population.

Summary statistics of lateral distal femoral angles will be calculated for each visit and new-onset potentially clinically significant knee lateral distal femoral angles (i.e. angles outside of the physiological range defined as 78.9 to 84.9 degrees). Listings will also be generated for subjects meeting PCS criteria overall and by PPC status.

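### Part C SAP 7.9.2: the last-case rule lets an unreadable or missing reading override a closed growth plate in the WBCT status table, and the Location list orders the same two outcomes the other way

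*SAP*

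**What the plan says.** Part C SAP 7.9.2 uses the whole-body CT scans to assess "bilateral hand/wrist and knee growth plate abnormalities on all subjects age < 18 years". The tabulation is set by one sentence, "Counts of abnormalities of epiphyseal growth plates (yes/no/not evaluable) detected will be summarized for each timepoint", followed by a parenthesis that gives the selection rule: "selecting the “last case” in the hierarchy for each abnormality, in order of the terms listed below".

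Two lists follow directly:

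- **Status** (open growth plates): Yes, Open; Yes, Partially Closed; No (Closed); Not Evaluable; Missing.
- **Location**, headed "Open Epiphyseal Growth Plates Location": Wrist or Knee; Wrist and Knee; Wrist Only; Knee Only; Not Evaluable; Closed.

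A new lead-in then introduces a third list, "Any Abnormality of Epiphyseal Growth Plates", with the terms Yes, No and Not Evaluable. The section does not say whether the rule collapses over side, over wrist and knee, or over reader.

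**The concern.** Over the first three status terms, taking the last one that applies is sensible: it picks the most advanced closure seen. The difficulty is that the list continues. Not Evaluable and Missing stand after Closed, so under the stated rule the absence of information outranks an observed closed plate.

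The table matters more than most descriptive ones. Section 1.2 records that premature physeal closure led to the partial clinical hold in subjects under 14, and Section 7.9 calls for bone safety to be analysed by closure status. A programmer who follows the rule exactly could move children with an observed closed plate into the uninformative rows, and would produce two adjacent blocks that disagree about the same child.

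**Working it through.** The SAP states no figure on this point, so there is none to reproduce. The check has two parts.

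**1. Apply the rule to each list.** Take two readings for one subject at one timepoint and let the later listed term win. Compare this with taking the most advanced closure state among evaluable readings.

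| Readings | Status list, literal rule | Most advanced evaluable state |
|---|---|---|
| Closed + Not Evaluable | Not Evaluable | Closed |
| Closed + Missing | Missing | Closed |
| Partially Closed + Not Evaluable | Not Evaluable | Partially Closed |
| Partially Closed + Missing | Missing | Partially Closed |
| Open + Not Evaluable | Not Evaluable | Open |
| Open + Missing | Missing | Open |

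These six pairs are the only ones on which the two rules differ. No pair becomes Closed under the literal rule that was not already Closed, so the closed count can stay the same or fall, never rise.

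In the Location list, Closed + Not Evaluable gives Closed, the reverse of the status result.

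The *percentage* closed has no fixed direction. Section 3 bases percentages on non-missing values. Let C be the number of closed subjects and N the number of non-missing subjects. Moving a closed subject to Missing gives (C − 1)/(N − 1), which is below C/N when C < N. Moving an open subject to Missing gives C/(N − 1), which is above C/N when C > 0.

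**2. How often it could bite.** Inputs, all assumed except the sites:

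- k, readings collapsed per subject: 4 if both wrists and both knees (7.9.2 is bilateral at two sites), 2 if the unit is coarser. The SAP does not state k.
- q, probability that a reading is unreadable or missing: not given; taken as 5%, 10% and 20%.
- Readings independent.

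A subject with a single closed, readable reading is overridden if any of the other k − 1 readings is unreadable:

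P(override) = 1 − (1 − q)^(k−1)

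| q | k = 2 | k = 4 |
|---|---|---|
| 5% | 1 − 0.95 = 5% | 1 − 0.95³ = 14.3% |
| 10% | 1 − 0.90 = 10% | 1 − 0.90³ = 27.1% |
| 20% | 1 − 0.80 = 20% | 1 − 0.80³ = 48.8% |

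Subjects may have more than one closed plate. With c the assumed probability that a readable site is closed:

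- literal rule: P(Closed) = (1 − q)^k × [1 − (1 − c)^k]
- evaluable-only rule: P(Closed) = 1 − [1 − (1 − q)c]^k

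For k = 4, c = 0.10, q = 5%, these are 0.2801 and 0.3292, so 1 − 0.2801/0.3292 = 14.9% of subjects with a readable closed plate are lost. With c between 0.10 and 0.30, the loss for k = 2 is 5–6%, 10–12% and 21–23% at q = 5%, 10% and 20%. For k = 4 it is 15–16%, 28–30% and 50–53%.

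**The case against.** The best defence is that the intent is visible. The readable states already run from open to closed, and Not Evaluable and Missing look like trailing display rows. The Location terms describe a subject, not a site, and they overlap, so a site-by-site collapse does not fit that list well. Section 7.9 also refers to a Bone Safety Management Plan for further detail. This makes an inadvertent error likely, but it does not remove it: the rule expressly follows the listed order, and a companion document could only conflict with that order.

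Three stronger readings are tempting and are not supported.

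- *Premature closure is under-counted.* The table counts open, partially closed and closed status, with no judgement on whether closure was premature. Premature closure is reported elsewhere without the last-case rule: "Listings of all subjects with premature growth plate closure will be provided" appears in 7.9.1, which also plans a summary in subjects under 18, and 7.1 adds a listing of serious events for it.
- *True abnormalities are turned into No.* If the rule governed the Any Abnormality list, Yes at one site and No at another would give No. But that list has its own lead-in, which does not repeat the rule, and any would ordinarily mean Yes if one site is Yes. The phrase in the rule about each abnormality, and the yes/no/not evaluable set in the sentence that carries it, leave an ambiguity worth closing, not an error to assert.
- *Section 7.9.1 uses the opposite convention, so the X-ray and CT tables must disagree.* The 7.9.1 rule, "For summaries across all timepoints, the worst case for a given subject will be used in the analysis", concerns changes pooled over timepoints. The 7.9.2 rule concerns status at each timepoint. Disagreement is not shown.

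Independence is also doubtful, since sites on one scan share image quality and positioning. If unreadable readings cluster within scans, a readable closed plate is less often accompanied by an unreadable one, and the figures above are too high.

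**Conclusion.** The defect is real and confined to the WBCT growth-plate tabulation in 7.9.2. As written, an unreadable or missing reading displaces a readable closed plate in the status block, and the Location block orders the same two outcomes in reverse. The closed count can therefore only be correct or too low, while the direction for the percentage closed is open because Open and Partially Closed subjects are displaced too.

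The size is unknown. It requires subjects with both readable and unreadable readings at one timepoint, and the SAP gives neither the unreadable rate nor the unit of collapse. The range of 5% to 49% for overriding a single closed reading rests on the assumed k and q and on independence. It shows that the effect need not be negligible, not that it occurred. The contradiction between the two lists needs no such assumption.

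**What to change.** Replace the last-case parenthesis in 7.9.2 with a rule that:

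1. names the unit over which readings are collapsed (side, wrist versus knee, reader);
2. selects the most advanced closure state among evaluable readings, with Closed above Partially Closed above Open;
3. assigns Not Evaluable or Missing only when no reading is evaluable;
4. uses one consistent order in the status and Location lists;
5. states that Any Abnormality is Yes if any evaluable site is Yes, so that the last-case rule cannot be applied to it.

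The cost is a few lines of SAP text and re-ordered category codes in the table program. No image needs to be re-read. The closed count in this table may rise.

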7.9.3 WBCTs Measurements of Femur and Tibia Lengths

Although the WBCT scans obtained in the trial are used primarily to quantify change in HO volume, they will also be used to assess the length of the femur and tibia bilaterally on all subjects age <18 years.

Two independent radiology reviewers will measure the femur and tibia lengths. The summary statistics of femur and tibia lengths (values and changes from baseline) for subjects < 18 years will be calculated for each visit for Enrolled Population. Femur and tibia length will be summarized for four different subgroups:

- Male, Age < 10, 10 - <14, 14 - < 18
- Female, Age < 8, 8 - <14, 14 - <18

Figures will include plots of the femur and tibia length by chronological age at assessment by gender.

Leg length discrepancies will be calculated by the difference in right and left femur and tibia lengths as measured by low-dose WBCT. Potential clinically meaningful leg length differences (ie, >1.5 cm difference) will be provided in a listing.

7.9.4 Evaluation of Bilateral Hips by WBCT Safety Read

Although the WBCT scans obtained in the Trial are used primarily to quantify change in HO volume, they will also be used to assess potential adverse effects on the femoral head related to avascular necrosis of the hip (AVN) in all subjects.

Two independent radiology reviewers will qualitatively assess the hip joints on WBCT scan to determine whether there is evidence of AVN. Discrepancies in the reads will be adjudicated. Each hip will be assessed for presence or absence of AVN and by specific abnormalities (i.e. cysts, subchondral lucency, subchondral collapse, osteosclerosis, flattening/collapse femoral head, ...), if present, the degree of change from the baseline scan and previous scan.

WBCT Hip abnormalities identified in WBCT safety reads will be summarized for Enrolled Population include the following:

- Number and proportion of subjects with No, Yes (possible, probable, or definite) AVN or not evaluable at baseline, and by specific abnormality
- Number and proportion of subjects with any new post-baseline or prior time point AVN, and by specific abnormality
- Number and proportion of subjects with any new post-baseline or prior time point worsening in AVN, and by specific abnormality
- Number and proportion of subjects with improvement in baseline or prior time point AVN, and by specific abnormality

Listings of any subject with possible, probable, definite AVN present will be provided.

7.9.4.1 Assessments for Spinal Health

WBCT scan assessments described above, will also be used to analyze spinal bone mineral density, bone strength, bone mineral content and fractures, utilizing biomechanical computed tomography (BCT) analysis. Additionally descriptive statistics will be provided for each timepoint.

8 Pharmacokinetics Data

Pharmacokinetics of palovarotene dosing will be assessed twice during flare-up based treatment: once during the 20-mg regimen at any time between Study Days 4 to 28, and once during the 10-mg regimen at any time between Study Days 32 to 84, for the first treated flare-up only. If this is not possible for the first treated flare-up, PK blood samples can be obtained during any subsequent flare-up dosing cycle. Pharmacokinetic blood samples will be collected at pre-dose and 3, 6, 10, and 24 hours post-dose. Subjects who underwent PK assessment under PVO-1A-202 Protocol Amendment 3 will not have PK assessed again under PVO-1A-202 Amendment 4.

Blood samples for PK assessment of non-flare-up dosing will be collected at the first 3-month safety assessment at pre-dose and 3, 6, 10, and 24 hours post-dose; if samples cannot be or were not obtained at the 3-month safety assessment, or if a subject is on flare-up based treatment, then the PK blood sample for non-flare-up based treatment can be obtained during any subsequent 3-month safety visit.

The allowed time deviation windows for pre-dose blood sample is 1 hour before dosing. The concentrations outside the sampling window will be listed but not used for PK parameter calculation and summary statistics. Plasma palovarotene concentrations will be summarized with descriptive statistics (number of non-missing values, arithmetic mean, standard deviation, standard error, coefficient of variation, geometric mean, median, minimum, and maximum).

All plasma concentrations below the limit of quantification (LOQ) will be set to zero for the purpose of calculating descriptive statistics. If at any time point, 1/3 or more of subjects have <LOQ values, descriptive statistics will not be calculated at that time point. PK concentrations will be imputed using the following:

- If 0-hour concentration missing, then 24-hour concentration used to replace the missing concentration.
- If 24-hour concentration missing, then 0-hour concentration used to replace the missing concentration.
- Invalid 24-hour concentrations replaced with the 0-hour concentrations. Twenty-four-hour concentrations are determined to be invalid if concentration is greater than the 10-hour value (i.e. assumed to have been obtained after next day dose instead of before next day dose).

For some subject who has both 0-hour and 24-hour concentration missing, the missing values will not be imputed. Data will be listed but excluded from PK parameter calculation.

If any other blood sample collections are missing, PK parameters will not be assessed. Actual sampling times will be used for the PK analysis, if available. Nominal sampling times will be used for descriptive statistics.

Individual concentration-time profiles for palovarotene will be presented (linear and semi-logarithmic scales). Arithmetic means (+/- standard deviation) concentration-time profiles will also be presented (linear and semi-logarithmic scales).

An exploration of the effects of body weight on PK will be performed as the data allows.

The PK analysis of palovarotene will be conducted using model-independent methods as implemented in WinNonlin™. The PK parameters analyzed will include $AUC_{0-24(ss)}$, $C_{max(ss)}$, $C_{min(ss)}$, $T_{max(ss)}$, $T_{min(ss)}$, CL_{ss}/F , λ_z , and $t_{1/2}$ at steady-state. The PK parameters are defined as follows in Table 8:

Table 8: PK Parameters

$AUC_{0-24(ss)}$	Area under the concentration versus time curve over the 24-hour dosing interval; calculated using linear trapezoid rule.
$C_{max(ss)}$	Maximum measured plasma concentration at steady-state.
$C_{min(ss)}$	Minimum measured plasma concentration at steady-state.
$T_{max(ss)}$	Time of maximum measured plasma concentration at steady-state, obtained by inspection.

$T_{\min(ss)}$	Time of minimum measured plasma concentration at steady-state, obtained by inspection.
CL_{ss}/F	Clearance defined as: Dose/AUC _{0-24(ss)} .
λ_z	Terminal rate constant
$t_{1/2}$	Apparent terminal elimination half-life; calculated as $\ln(2)/\lambda_z$. The number of data points included in the regression will be determined by visual inspection, but a minimum of three data points in the terminal phase, excluding C_{\max} , will be required to estimate λ_z .

The λ_z will not be presented for subjects who do not exhibit a terminal elimination phase in their concentration-time profiles. In order to estimate the first-order terminal elimination constant, λ_z , linear regression of concentration in logarithm scale vs. time will be performed using at least 3 data points. Uniform weighting will be selected to perform the regression analysis to estimate λ_z .

The constant λ_z will not be assigned if one of the following happens:

- T_{\max} is equals to one of the 3 last data points,
- The estimated elimination rate indicates a positive slope, or
- The terminal elimination phase is not linear (as appears in a semi-logarithmic scale) based on visual inspection.

PK parameters will be summarized with descriptive statistics (number of non-missing values, arithmetic mean, standard deviation, standard error, coefficient of variation, geometric mean, median, minimum, and maximum).

9 Changes from Protocol introduced in SAP Version 0.3 (13 July 2020)

For the purposes of clarity and consistency of nomenclature, the study populations described in the protocol were revised to align with the study populations from Part B.

The protocol describes the primary efficacy comparison of outcomes from data collected from the Natural History Study (NHS) and the Phase 2 study. These comparisons will be performed in a future analysis and the analysis described in this SAP will instead focus on comparisons solely from Study PVO-1A-202 Part C.

10 Changes from Protocol introduced in SAP Version 1.1 (16 December 2022)

The following substantive changes from protocol Section 8 ('Statistical and Analytical Plans') are documented:

Location/Section Number	Change	Rationale
8.1 General Methods	Per the protocol, data from Part B and Part C were to be combined. Unless otherwise specified, Part B and Part C data will now be summarized separately, with the focus of the final CSR being data collected after	Data were collected in separate clinical databases. The Interim CSR summarized Part A, Part B and Part C independently, due to the substantial differences in the

	28 February 2020, i.e. cutoff for the interim CSR.	dosing regimens in each part of the study.
8.3 Study Populations	
This SAP amendment adds Restart Full Analysis Set (RFAS) includes all enrolled subjects in the FAS who restarted palovarotene therapy after January 2020 and have at least two HO volume measurements in Part C trial on or after restart, with the first such WBCT imaged at least 30 days after the end of the previous flare-up.
 
The Per-Protocol Set (PPS) is not intended to be summarized.
	
The RFAS population is most similar to those described in other palovarotene studies.
 
Due to the small sample size, particularly when the additional restriction that baseline WBCT must be taken at least 30 days after the end of the previous flare-up (as was the case for Study 301 and NHS), formal per-protocol analyses are not planned to be performed.

8.7.1 Primary Efficacy	
Per the protocol, the primary efficacy analysis was to be a wLME comparing annualized HO volume collected in Study 202 Parts B and C with that in Study 001 (NHS). In the final CSR, propensity-score based comparisons of Study 202 Part B and Part C vs NHS, as well as Study 202 Part C alone vs NHS, will be performed. Additional analyses more similar to those specified in the protocol, e.g. GEE, will also be performed.
	
Efficacy summaries will be based on analyses prepared at the request of regulators.

8.8.1 Adverse Events	
Per the protocol, retinoid associated adverse events were to be summarized. Consistent with the interim CSR, this is no longer planned.
	
The pre-specified retinoid AEs outlined in the protocol did not encompass all AEs which might be considered retinoid associated AEs. SMQ analysis was more comprehensive.

11 Changes from SAP Version 0.3 (13 July 2020) introduced in SAP Version 1.1 (16 Dec. 2022)

The following key substantive changes from SAP Version 0.3 are documented:

Location/Section Number	Change	Rationale
1.1 Context for Version 1.1	Amendment is preparation for final CSR.	Version 0.3 described the data summaries to be used for the interim CSR.
3.1.4 Baseline for Subjects who Restarted Palovarotene after dosing interruption in Part C	Definition added.	Needed for RFAS summaries.
3.4 Adjustment for Covariates	Efficacy analyses comparing annualized new HO in Study 202 vs NHS requested by FDA are described.	Efficacy was summarized descriptively in the interim CSR.
4.4 Flare-up Per Protocol Population	Formal per-protocol analyses are not planned to be performed.	See Section 10
4.6 Restart Full Analysis Set	RFAS added.	See Section 10
4.7 Part D Analysis Set	Part D Analysis Set added.	Needed to summarize post-interruption data for skeletally immature subjects who stopped taking palovarotene before completion and had imaging to allow for their study.
7 Safety Data	Safety data summaries in the final CSR will be based on the safety data presentations in recent documents, including the Safety Update included in the NDA and the Day 90 Safety Update; the primary difference will be that those summaries included data from all palovarotene studies, while the Study 202 presentations will only include data collected in Study 202.	Given the complicated history of palovarotene, basing the CSR summary on previous discussions will ensure consistency.

12 References

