7.9 Columbia-Suicide Severity Rating Scale

Suicidal ideation and behavior will be assessed using the Columbia-Suicide Severity Rating Scale (C-SSRS).

Data listings will be provided for (1) all C-SSRS results; and (2) for subjects reporting any type 4 or type 5 suicidal ideations.

8 Pharmacokinetics Data

Pharmacokinetics will be assessed within 7 days of flare-up based treatment initiation and at the end of treatment for the first treated flare-up. Blood samples will be taken at 0, 3, 6, 10, and 24 hours post-dose.

Plasma palovarotene concentrations will be summarized with descriptive statistics (number of non-missing values, arithmetic mean, standard deviation, standard error, coefficient of variation, geometric mean, median, minimum, and maximum). All plasma concentrations below the limit of quantification (LOQ) will be set to zero for the purpose of calculating descriptive statistics. If

at any time point, 1/3 or more of subjects have <LOQ values, descriptive statistics will not be calculated at that time point. PK concentrations will be imputed using the following:

- If 0-hour concentration missing, then 24-hour concentration used to replace the missing concentration.
- If 24-hour concentration missing, then 0-hour concentration used to replace the missing concentration.
- Invalid 24-hour concentrations were replaced with the 0-hour concentrations. Twenty-four-hour concentrations were determined to be invalid if concentration is greater than the 10-hour value (i.e. assumed to have been obtained after next day dose instead of before next day dose).

If any other blood sample collections are missing, PK parameters will not be assessed. Actual sampling times will be used for the PK analysis, if available. Nominal sampling times will be used for descriptive statistics.

Individual concentration-time profiles for palovarotene will be presented (linear and semi-logarithmic scales). Arithmetic means (+/- standard deviation) concentration-time profiles will also be presented (linear and semi-logarithmic scales).

An exploration of the effects of body weight on PK will be performed as the data allow.

The PK analysis of palovarotene will be conducted using model-independent methods as implemented in WinNonlin™. The PK variables analyzed will include $AUC_{0-24(ss)}$, $C_{max(ss)}$, $C_{min(ss)}$, $T_{max(ss)}$, CL/F , λ_z , and $t_{1/2z}$ at steady-state. The PK variables are defined as follows:

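### Setting concentrations below the limit of quantification to zero makes the geometric mean zero or undefined at any reported time point that contains one (Part B and Part C SAPs, Section 8)

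*SAP*

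**What the plan says.** Both SAPs treat plasma concentrations in Section 8, Pharmacokinetics Data, and the wording on this point is the same.

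- **Statistics.** In Part C: "Plasma palovarotene concentrations will be summarized with descriptive statistics (number of non-missing values, arithmetic mean, standard deviation, standard error, coefficient of variation, geometric mean", followed by the median, minimum and maximum. Part B has the same list.
- **Values below LOQ.** In both parts: "All plasma concentrations below the limit of quantification (LOQ) will be set to zero for the purpose of calculating descriptive statistics".
- **Suppression.** In Part C: "If at any time point, 1/3 or more of subjects have <LOQ values, descriptive statistics will not be calculated at that time point". Part B has the same threshold: "at any time point, 1/3 or more of subjects have <LOQ values, descriptive statistics will not be calculated at that time point".
- **Sampling.** In Part C: "Pharmacokinetic blood samples will be collected at pre-dose and 3, 6, 10, and 24 hours post-dose". Part B uses 0, 3, 6, 10 and 24 hours.

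Neither Section 8 says what happens to the geometric mean when a zero is present: whether zeros are left out, replaced, or the statistic reported as not calculable.

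**The concern.** The zero rule and the list of statistics do not fit together. Zero is a usable, if crude, value for an arithmetic mean, standard deviation or median. A geometric mean cannot take a zero and still describe the other values.

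A programmer following the text literally will print 0 or get a missing result. One who sees the difficulty must improvise, and two programmers may choose differently. At stake is whether the geometric means in the concentration tables can be read, and whether the Part B and Part C tables follow one convention. Pre-dose and 24 hours are the natural places for low values. Both SAPs also copy the 0-hour value to 24 hours, or the reverse, when one of them is missing, so one low trough can put a zero at both times.

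**Working it through.** The SAPs state no figure on this point, so there is none to reproduce. The check has four steps.

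**1. The algebra.** The geometric mean is (x₁·x₂·…·xₙ)^(1/n) = exp[(1/n)·Σ ln xᵢ]. If any xᵢ = 0, the product form gives 0 and the log form meets ln 0, which is undefined. As an illustration on assumed data (20 log-normal values, median about 10, log-SD 0.5), the geometric mean is 10.19. With the lowest value set to zero it is 0, while the arithmetic mean is 10.34 and the median 10.89.

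**2. What the one-third rule lets through.** Statistics are reported when the number k of values below LOQ satisfies 3k < n. Reported time points can therefore contain these numbers of zeros:

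| n | k still reported |
|---|---|
| 3 or fewer | none |
| 4 to 6 | 1 |
| 10 | 1 to 3 |
| 20 | 1 to 6 |
| 30 | 1 to 9 |

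The rule removes the problem only at n ≤ 3.

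**3. How often it would bite.** The rate p below LOQ and the number sampled are not given, so both are assumed, with samples independent. The chance that a time point is reported and contains a zero is P(1 ≤ K ≤ kmax) = P(K ≤ kmax) − (1 − p)ⁿ, where K is binomial(n, p) and kmax is the largest k with 3k < n.

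- n = 10, p = 10%: 0.3874 + 0.1937 + 0.0574 = 0.6385, or 64%.
- n = 20, p = 20%: 0.9133 − 0.0115 = 0.9018, or 90%.

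| n | p = 5% | p = 10% | p = 20% | p = 30% |
|---|---|---|---|---|
| 10 | 40% | 64% | 77% | 62% |
| 20 | 64% | 88% | 90% | 61% |

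The figures fall at 30% because more time points are then suppressed (39% of them at n = 20).

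**4. The bias of a substitute.** Assume a log-normal distribution with CV 60% and geometric mean 1, so that s = √ln(1 + 0.6²) = 0.5545, with the LOQ at the p-th quantile z on the standard normal scale and φ the standard normal density. Using LOQ/2, the log of the geometric mean shifts by s·φ(z) + p·(s·z − ln 2). At p = 10%, z = −1.2816 and φ(z) = 0.1755, giving 0.0973 + 0.10·(−0.7106 − 0.6931) = −0.0431, or −4%. The same formula gives −2%, −4%, −7% and −10% at 5%, 10%, 20% and 30%.

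**The case against.** The strongest reply is that little hangs on this. The statistic is descriptive and no inference uses it. Mean concentration profiles are plotted as arithmetic means, which the zero rule leaves computable. A printed 0 or blank would be obvious beside the arithmetic mean and median. With steady-state sampling and an unknown LOQ, values below it may never occur. All of this stands, and it limits the weight of the point, but it does not make the rule workable when such a value does occur.

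It can also be said that Part C Section 1.2 has the PK analysis performed separately, so a convention might sit elsewhere. The same section says the PK analysis is described in this SAP, and the description given is the one that fails.

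A reader might infer more than the documents support:

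- **That a comparison of troughs across the 5, 10 and 20 mg regimens is compromised.** Neither SAP plans one. Both plan only an exploration of body weight and PK as the data allow, naming neither troughs nor geometric means.
- **That the 5 mg dose is worst affected.** No concentrations and no LOQ are given, so this cannot be shown.
- **That the geometric mean of Cmin(ss) fails in the same way.** Part C states that "PK parameters will be summarized with descriptive statistics (number of non-missing values, arithmetic mean, standard deviation, standard error, coefficient of variation, geometric mean, median", but that sentence carries no zero rule. The rule is set out for plasma concentrations. The SAPs are silent on values below LOQ when parameters are derived, which is a separate matter.
- **That the geometric mean would be biased upward by 6% to 32%.** Under the model in step 4, that is the effect of dropping zeros at rates of 5% to 30%. The text says to set values to zero, so followed literally it gives 0 or no result, not an inflated mean.

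**Conclusion.** The point holds for the concentration summaries in both parts. At every reported time point with at least one but fewer than one third of subjects below LOQ, the plan as written yields a geometric mean that is zero or undefined. That conclusion needs no assumption. How often it happens rests on assumed rates and group sizes: about 40% to 90% of time points for rates of 5% to 20% and n of 10 to 20, and none if no sample falls below LOQ. The consequence is an uninformative cell in a descriptive PK table. No efficacy or safety conclusion depends on it. It is a minor correction, worth making because a stated rule gives a wrong number when followed exactly.

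**What to change.** In Section 8 of both SAPs:

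1. Limit the zero rule to the arithmetic mean, SD, SE, CV, median, minimum and maximum of concentrations.
2. For the geometric mean of concentrations, prespecify one of two rules: report it as not calculated when any value is below LOQ, or use a single stated non-zero substitute such as LOQ/2.
3. Show the number of values below LOQ in each cell.

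The cost is one sentence in each SAP and a line of programming, with no new data. Reporting it as not calculated loses the statistic at affected time points. LOQ/2 keeps it at the price of the 2% to 10% downward bias worked out above, and the arithmetic and geometric means in one row then rest on different substituted values, which a table footnote should state. LOQ/2 is one convention among several; what matters is that one rule is fixed in advance and used in both parts.
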